## ABBREVIATIONS USED IN THE PROTOCOL

Abbreviation	Term
AE	Adverse Event
SAE	Serious Adverse Event
GCP	Good Clinical Practice
IRB	Institutional Review Board
ICF	Informed Consent Form
HIPAA	Health Insurance Portability and Accountability Act of 1996
EOS	End of Study
FDA	Food and Drug Administration
US	United States
EMR	Electronic Medical Record
SOA	Schedule of Activities
SAS	Statistical Analysis System
IM	Intramuscular
SC	Subcutaneous
TENS	Transcutaneous Electrical Nerve Stimulation
LB	Long Buccal
IAN	Inferior Alveolar Nerve
FAS	Facial Anxiety Scales
VAS	Visual Analog Scale
SSI	Symptom Severity Index
$H_0$	Null Hypothesis
$H_A$	Alternative Hypothesis
n=	Number
NS	Normal Saline
BMI	Body Mass Index
NSAIDs	Nonsteroidal Anti-Inflammatory Drugs
BP	Blood Pressure

## 1 INTRODUCTION

### 1.1 Background and Significance

Each year in the United States, millions of individuals undergo medical procedures involving needles, including intramuscular (IM) injections, subcutaneous (SC) injections, and fingersticks for blood glucose monitoring and other point of care testing. These procedures are essential for administering vaccines, managing chronic conditions, and monitoring health. However, a significant portion of the population experience a fear of needles due to the associated pain, which can impact their willingness to undergo these necessary medical interventions. This fear can result in missed vaccinations, poor adherence to medication regimens, and inadequate monitoring of conditions, such as diabetes. Understanding the prevalence and impact of needle fear due to pain is crucial for developing strategies to improve patient compliance and overall health outcomes.

Pain is transmitted through nociceptors, derived from neural crest cells in the spinal cord during gestation and relayed by the thalamus. While the full mechanism of pain is unclear, the 'Gate Control Theory of Pain', introduced by Melzack and Wall in the 1960s, is widely used. This Theory suggests that open spinal gates allow for painful stimuli to permeate through the body while closed gates halt that process . This theory also highlights two types of afferent fibers that mediate the pain stimuli – fast-transmitting myelinated A fibers (pricking pain) and slow-transmitting unmyelinated C fibers (burning pain) .

Pain associated with needle-based procedures can be reduced through a variety of non-interventional methods, including distraction techniques, cooling, and tactile stimulation. One such method gaining attention is vibration therapy (also known as vibration anesthesia), which uses localized mechanical stimulation to interfere with pain signal transmission and reduce perceived discomfort. Vibrations serve as a competing sensory input that can help block pain signals from reaching the brain, consistent with the gate control theory of pain (eg. closed gate process). Over the years, vibration devices such as the Transcutaneous Electrical Nerve Stimulation (TENS) Unit machine (1974), Buzzy (2009), and Vibracool (2015), have demonstrated that non-painful stimuli effectively be used to reduce the perception of pain.

DigiVibe is a cordless, handheld device designed to reduce the pain caused by needles that is a U.S. Food and Drug Administration (FDA) registered device to be used to reduce

the pain associated with fingerstick blood glucose testing. By applying targeted vibrations to the skin prior to a needle stick, it interferes with pain signal transmission to the brain, making the process more comfortable for users.

A prospective, randomized study comparing vapocoolant (cold) spray versus vibration anesthesia evaluated pre-injection (expected pain) and a post-injection pain (actual perceived pain). One-hundred and eighty (180) subjects with arthritis, tendinopathy, or compression neuropathy of the hand, wrist, or elbow were randomized to one of three groups – no anesthesia (n=60), injection with vapocoolant spray (n=60), and injection with vibratory anesthesia (n=60). Subjects were provided a 10-point Likert scale pre-injection, to assess expected pain, and a post-injection, to assess actual perceived pain.

Pre-injection pain scores for no anesthesia, vapocoolant, and vibration were 5.57, 5.32 (p-value 0.01470), and 5.73 (p-value 0.0446), respectively. Post-injection pain scores were the following for no anesthesia 5.18 (CI: -1.22 to 0.45), cold spray 4.12 (p-value: 0.1470; CI: -1.95 to 0.45), and vibration anesthesia 4.18 (p value 0.0446; CI: -2.34 to 0.76). These results suggest that vibration anesthesia could be a useful adjunct for injections of the hand, wrist, or elbow – which has been consistent with previously published data .

The Vibration Device to Control Injection Discomfort trial analyzed the discomfort level of 60 subjects (30 men and 30 women) who needed local anesthesia for intraoral long buccal (LB) and inferior alveolar nerve (IAN) injections. This study evaluated pain and anxiety levels during anesthesia administration with the DentalVibe® Injection Comfort System, which uses pulsation to reduce discomfort during injection administration. Anxiety prior to an injection was measured using the facial anxiety scales (FAS), acute pain intensity during injection was assessed with the Visual Analog Scale (VAS), and symptom history over the past six months was recorded using the Symptom Severity Index (SSI) . The study did not showcase statistically significant differences in any measures. However, individuals who did not receive DentalVibe® had higher scores across all measures for both injections indicating that there was a clinically meaningful reduction in pain with the use of DentalVibe® in combination with injections during dental anesthesia.

## **1.2 Risk Assessment**

### DigiVibe

The DigiVibe device is considered to be safe and noninvasive and the potential risks to subjects in this study are minimal, if any.

### Skin Irritation or Discomfort

Prolonged or overly intense use of DigiVibe in one area of the skin could cause temporary redness, bruising, or minor soreness, specifically in patients with sensitive skin.

### Normal Saline and Injections

Normal saline will be used for intramuscular and subcutaneous injections and, while it is an inert and widely used solution, intramuscular and subcutaneous injections may have some potential risks, if any.

As with any standard of care injections, subjects may experience soreness, pain, redness, swelling, or tenderness at the injection site. Mild bruising or local irritation may also occur with a potential for minor bleeding at the injection site. Though rare, there is a small risk of skin or soft tissue infection at the injection site.

## **2 ETHICS**

### **2.1 Good Clinical Practice (GCP)**

This study will be conducted in accordance with Good Clinical Practice (GCP), in accordance with the United States Code of Federal Regulations, Title 21, Part 50 (21CFR50). The study will be conducted in compliance with the protocol.

All potential protocol deviations or violations must be reported to the IRB immediately. A protocol deviation or violation is defined as a violation of the GCP guidelines regarding the study protocol, which is likely to significantly affect the safety of the subjects in the

study or the scientific validity of the study. Study staff involved in conducting this study will be qualified by education, training, and experience to perform their respective tasks and this study will not use study staff where there has been scientific misconduct or fraud (e.g., loss of medical licensure, debarment).

## **2.2 Institutional Review Board (IRB)**

Before initiation of the study, the investigator must have received IRB approval for the protocol, Informed Consent Form (ICF), subject recruitment materials (e.g., advertisements), and any other written information to be provided to subjects.

During the clinical study, any amendment to the clinical trial protocol must be submitted to the IRB before implementation, unless the change is necessary to eliminate an immediate hazard to the subjects, in which case the IRB should be promptly informed. The IRB should also be informed of any event likely to impact the safety of subjects in the clinical trial. The investigator must send a progress report to the IRB at least annually, as well as a summary of the clinical trial's outcomes at the end of the clinical trial.

## **2.3 Informed Consent**

The investigator will ensure that the ICF includes all elements required by GCP and applicable regulatory requirements, as well as follow the ethical principles within the Declaration of Helsinki. The investigator will ensure that the ICF is reviewed and approved by the IRB prior to use in a clinical trial.

The Investigator, or a person designated by the Investigator, should fully inform the subject of all pertinent aspects of the clinical trial including the purpose, potential risks, required procedures, etc. in which they volunteer to participate. All subjects should be informed about the study in a language and at a level they are able to understand. In circumstances where consent cannot be given to subjects, their legally acceptable representatives must be clearly and fully informed about the purpose, potential risks, required procedures, etc. regarding the clinical trial in which the subject will participate.

Prior to a subject's participation in the clinical trial, the written ICF should be signed and dated personally (by the subject) or by the subject's legally acceptable representative and by the person who conducted the informed consent discussion. A copy of the signed and dated written ICF will be provided to the subject.

### **3 HYPOTHESIS**

Null Hypothesis ( $H_0$ ): DigiVibe vibration anesthesia has no clinically significant impact on pain scores.

Alternative Hypothesis ( $H_A$ ): DigiVibe vibration anesthesia has a clinically significant impact on pain scores.

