## 4.2 Study Objectives / Endpoints

Objective	Endpoint
Primary	
To demonstrate if the use of DigiVibe is superior to no intervention in reducing pain scores during intramuscular injections, subcutaneous injections, and fingersticks.	Difference between DigiVibe and no intervention on pain scores.

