## 4.9 Data Analysis

### 4.9.1 Statistical Analysis Plan

Demographics and baseline characteristics of study subjects will be summarized, as will VAS pain scores for the intervention (DigiVibe) and standard care. The primary analysis will be a paired t-test or Wilcoxon signed-rank test (depending on normality of VAS scores) to compare pain scores between standard care and DigiVibe. These tests will be performed individually for each of the injection sites (fingerstick, SC, IM).

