#### **4.9.2 Statistical Power and Sample Size Considerations**

For any of the three (3) injection sites individually, a sample size of 20 patients achieves  $\geq 80\%$  power to detect a mean of paired differences of 1.0 with an estimated standard deviation of differences of 1.5 and with a significance level ( $\alpha$ ) of 0.05 using a two-sided paired t-test. A smaller difference (e.g., 0.75) would be detectable with power  $\geq 88\%$  at an  $\alpha=0.05$  using the same test, if the standard deviation is 1.0.

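### Section 3 states the hypotheses as a clinically significant impact, but the planned tests can only show a difference from zero, and the plan gives no threshold or confidence interval to bridge the gap

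*Combined protocol and SAP*

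**What the plan says.** Section 3 of the combined protocol and SAP gives the null hypothesis as "DigiVibe vibration anesthesia has no clinically significant impact on pain scores" and the alternative as "DigiVibe vibration anesthesia has a clinically significant impact on pain scores". Neither carries a number or a direction.

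The other sections are framed differently:

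- **Section 4.2, objective:** "To demonstrate if the use of DigiVibe is superior to no intervention in reducing pain scores", for the three procedures. The endpoint is "Difference between DigiVibe and no intervention on pain scores", with no threshold and no responder definition.
- **Section 4.9.1, analysis:** "The primary analysis will be a paired t-test or Wilcoxon signed-rank test (depending on normality of VAS scores"), and "These tests will be performed individually for each of the injection sites". No non-zero null value is given. The descriptive output covers demographics and baseline characteristics, "as will VAS pain scores for the intervention (DigiVibe) and standard care". An estimate or confidence interval for the paired difference is not mentioned.
- **Section 4.9.2, power:** 20 subjects are said to give at least 80% power "to detect a mean of paired differences of 1.0 with an estimated standard deviation of differences of 1.5", two-sided at 0.05. A second scenario (difference 0.75, SD 1.0) is said to give at least 88%. Neither difference is described as clinically significant.

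The description of the VAS in section 4.6 gives a 0 to 10 scale and no important difference on it.

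**The concern.** A hypothesis test supports only the alternative that it was built to test. A paired test against zero can reject the statement that there is no difference. It cannot reject the statement that there is no clinically significant difference, because that null also covers every non-zero effect too small to matter. Section 3 is the only place where the plan states its hypotheses formally. Taken as written, a p-value below 0.05 at any site would be read as acceptance of a clinically significant impact.

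The risk of over-reading is real here. Section 1.1 describes a dental vibration-device study with no statistically significant differences and still calls its result clinically meaningful, with no threshold named. Section 4.1 says the results should help providers choose how to manage pain, and section 7 foresees publication. Both uses depend on the size of the effect.

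There is a lesser problem of direction. An impact could be more pain as well as less, so the alternative as worded would also be met by a significant result against the device.

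**Working it through.** **Inputs.** From section 4.9.2: n = 20 pairs, two-sided alpha 0.05, mean difference 1.0 with SD of differences 1.5, or mean difference 0.75 with SD 1.0.

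**1. Which null does the power calculation use?** Take a null difference of zero and the exact noncentral t with 19 degrees of freedom and noncentrality (difference/SD) × √20.

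| Scenario | Noncentrality | Power, zero null | Plan states |
|---|---|---|---|
| 1.0, SD 1.5 | (1.0/1.5) × 4.472 = 2.98 | 80.7% | at least 80% |
| 0.75, SD 1.0 | 0.75 × 4.472 = 3.35 | 88.9% | at least 88% |

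Both stated figures reproduce. The values 1.0 and 0.75 are therefore effects to be detected against zero. They are not thresholds for a decision, and since there are two of them, neither can be taken as an implied threshold.

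**2. How small an observed difference gives p<0.05?** The cut-off for the paired t-test is t(0.975, 19) × SD/√20 = 2.093 × SD/4.472.

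| SD of differences | Cut-off | 95% CI at the cut-off | Share of planning difference |
|---|---|---|---|
| 1.5 | 0.702 | 0 to 1.404 | 0.702/1.0 = 70% |
| 1.0 | 0.468 | 0 to 0.936 | 0.468/0.75 = 62% |

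At the cut-off the interval reaches down to zero. Even an observed difference of exactly 1.0 with SD 1.5 has a 95% CI of 1.0 ± 0.702, or 0.30 to 1.70.

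**3. What would a test of the worded hypothesis need?** The documents give no threshold, so the margins M below are assumptions for illustration only. The test is of a difference no greater than M, one-sided 0.025, with true difference 1.0 and SD 1.5.

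| Assumed M | Power at n = 20 | n for 80% power |
|---|---|---|
| 0.25 | 56% | 34 |
| 0.5 | 29% | 73 |
| 0.75 | 10.5% | 285 |

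On these assumptions, 20 subjects would not be enough for a test of the hypothesis as section 3 words it.

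**4. Direction.** With no true effect, a two-sided 0.05 test is significant in the direction of more pain in 2.5% of trials per site. At the planning effects this probability is below 0.000001 (7.8e-7 and 1.2e-7).

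**5. Can a reader recover the interval from the planned output?** No. Means and SDs reported separately for each condition do not give the SD of the paired differences, which the interval requires.

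**The case against.** The strongest reply is that this is a fault of wording and not of analysis. Sections 4.1, 4.2, 4.9.1 and 4.9.2 agree with one another, and only two sentences in section 3 are out of step. No section ties a p-value to a clinical claim, and section 4.2 supplies the intended conclusion, which is superiority. Direction is also clear from sections 4.1 and 4.2, and a two-sided test with a directional objective is ordinary practice. The figures in steps 2 and 4 are generic: any trial with about 80% power reaches significance at about 70% of its planning difference (1.96/2.80 = 0.70), and 2.5% is one tail of any two-sided 0.05 test. Finally, removing the clinical term from the hypotheses does not supply the missing threshold.

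Much of this stands. The test of zero difference is valid, the power statement is correct, and direction is a secondary matter. The generic figures show the scale of the gap and are not evidence of a separate fault. Because the documents do not say whether 0.70 or 0.47 points matters to patients, it cannot be shown that any particular conclusion would be wrong.

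The reply does not remove the mismatch. Formal hypotheses define what rejection means whether or not a later section repeats it, and these define it as something the test cannot show. Naming the difference as the endpoint in section 4.2 does not commit the analysis to reporting it with an interval. Leaving the threshold out of the remedy is deliberate: the documents give no basis for choosing one.

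**Conclusion.** The concern holds. The hypotheses in section 3 do not match the objective, tests and power calculation, and nothing else in the plan connects a significant test to clinical significance. A result at p<0.05 could rest on an observed difference as small as 0.70 points (SD 1.5) or 0.47 points (SD 1.0) on the 0 to 10 scale, with an interval reaching zero. Those figures assume 20 complete pairs, the paired t-test and the plan's own SDs. Whether such differences are clinically important is not stated and is not judged here. The fault affects what the trial may conclude, not the validity of its test of zero difference. It should be corrected.

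**What to change.** 1. **Section 3.** Replace the hypotheses, for each site, with wording such as: *H0: VAS pain does not differ between DigiVibe and no intervention (paired differences centred on zero). HA: VAS pain differs (two-sided). Superiority is concluded only if the result is significant in the direction of less pain with DigiVibe.*
2. **Section 4.9.1.** Add, per site, an effect estimate with a 95% CI that matches the test used: the mean paired difference with its t interval for the paired t-test, or the Hodges-Lehmann estimate with its interval for the Wilcoxon test. The match matters. In 20,000 simulated trials (n = 20, mean 1.0, SD 1.5, distribution shapes assumed), the t interval and the exact Wilcoxon p-value disagreed about zero in 4.7% with normal differences and 8.6% with heavy-tailed ones (t with 3 degrees of freedom, scaled to SD 1.5).
3. **Also in section 4.9.1.** State that clinical significance will not be claimed from p<0.05 alone.

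The cost is a wording amendment and one estimate with its interval per site. Test and sample size stay as they are. With the direction rule, power remains 80.7% and 88.9%. The price is a more modest conclusion after a significant result.

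If the sponsor wants to keep a claim of clinical significance, the alternative is to specify and justify an important VAS difference in advance and judge the interval against it. Step 3 of the working shows what that could cost in subjects.

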### **4 STUDY DESIGN**

#### **4.1 Description**

This is a single-center, unblinded, prospective, cross-over study. The study population will include twenty (n=20) healthy subjects (10 men and 10 women) over the age of 18 with a self-reported fear/dislike of needles. Subjects who qualify for the study based on the study inclusion and exclusion criteria and who consent to participate in the study will undergo two (2) intramuscular (IM) injections in the deltoid muscle, two (2) subcutaneous (SC) injections in the abdomen, and two (2) fingersticks with a lancing device in the middle finger. Normal Saline (NS) will be used for the IM and SC injections. The study duration per subject is expected to be one (1) day.

While the complete mechanisms of pain and pain diversion are not completely understood, DigiVibe locally targets the skin's pain receptors. Therefore, it is proposed that the vibrations from the DigiVibe device will counteract and/or lessen the pain around the injection site. This study will determine whether the use of DigiVibe during a procedure requiring injections provides greater reduction in pain than injections with no intervention (standard of care). This information will aid healthcare providers in selecting the best approach to management of pain in patients who must undergo injections that could cause pain and may benefit from additional pain reduction.

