Subjects will then undergo two IM injections. Subjects will undergo alternating assignments to either a 25-gauge 1 inch needle or a 30-gauge 1 inch needle in the upper arm deltoid muscle. The alternating assignment should be performed separately for the males and females so there is an equal distribution of males and females assigned to 25-gauge and 30-gauge. The alternating assignments must be documented. The first IM injection will be performed with no intervention (as per standard of care). Immediately following the injection, subjects will be provided with the VAS pain scale and asked to assess their level and pain and document it by circling the level of pain. After waiting 5 minutes, the DigiVibe device will be applied to the other deltoid muscle for 20 seconds and then the second IM injection will be immediately performed with the DigiVibe device still vibrating the injection site during the entire injection process. Immediately following the IM injection, subjects

will be provided the VAS pain scale and asked to assess their level and pain and document it by circling the level of pain.

Subject AEs will be recorded.

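### Sex is fixed at 10 men and 10 women but left out of all three primary tests, so some precision is forgone if the device effect differs materially by sex (minor)

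*Combined protocol and SAP*

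**What the plan says.** Section 4.1 sets the sample as "twenty (n=20) healthy subjects (10 men and 10 women) over the age of 18 with a self-reported fear/dislike of needles", so the sex split is fixed in advance. Section 4.6 (Demography) records sex. In section 4.5 (Visit 1), the needle gauge for the IM injections alternates within sex: "The alternating assignment should be performed separately for the males and females so there is an equal distribution of males and females" in each gauge group. Each subject keeps the same gauge for both IM injections.

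Section 4.9.1 states: "The primary analysis will be a paired t-test or Wilcoxon signed-rank test", chosen by the normality of the scores and run once for each of fingerstick, SC and IM. It has no sex term, no stratification and no estimate of the device effect by sex. Section 4.9.2 says: "For any of the three (3) injection sites individually, a sample size of 20 patients achieves" at least 80% power for a mean paired difference of 1.0 with an SD of differences of 1.5 (two-sided 5%). It gives one SD for everyone.

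**The concern.** Pairing removes any difference between men and women in how much a needle hurts. It does not remove a difference in how much the device helps. When the numbers of men and women are fixed, that second difference is not a source of sampling error in the overall mean, because every repeat of the trial would again have 10 of each. The SD of all 20 differences still contains it. The paired t-test then uses too large a standard error, its interval is wider than necessary, and some power is given up. The balance built in at enrolment is not used where it could help.

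What is at stake is efficiency. In addition, a sex-balanced trial has no pre-specified estimate of whether the device effect differs by sex.

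**Working it through.** **Inputs from the documents.** n = 20, split 10/10 (4.1). Mean difference 1.0, SD of differences 1.5, two-sided alpha 0.05 (4.9.2).

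**Assumed input.** d is the gap between men and women in device effect, in VAS points. The documents give no value, so a range is shown. Differences are taken as normal.

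**Step 1: the plan's own figure.** Noncentral t with noncentrality 1.0/1.5 × √20 = 2.98 and 19 df gives 80.7% power. The second scenario (0.75, SD 1.0) gives 88.9%. Both agree with 4.9.2.

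**Step 2: the two variances.** Let s be the SD of differences within each sex.
- True variance of the mean under the fixed split: s²/20.
- Expected variance of the pooled differences: s² + (20/19) × d²/4. The t-test divides this by 20.
- Average inflation of the standard error: √(1 + (20/19) × d²/(4s²)).

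**Step 3: hold the total SD at 1.5**, reading 4.9.2 as written, so s = √(1.5² − d²/4). For d = 1.0, s = √(2.25 − 0.25) = 1.414 and the inflation is √(1 + 0.2632/2.0) = 1.064. For d = 1.5, s = √(2.25 − 0.5625) = 1.299 and the inflation is √(1 + 0.5921/1.6875) = 1.162.

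**Step 4: power at mean 1.0**, pooled t-test (19 df) against the same mean tested on the within-sex SD (18 df). Values are from simulation with 200,000 trials per case; at d = 0 they are the noncentral t values.

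| Gap d (assumed) | Standard error too wide by | Power, pooled | Power, sex-adjusted |
|---|---|---|---|
| 0 | 0% | 80.7% | 80.5% |
| 0.25 | 0.4% | 80.7% | 80.7% |
| 0.5 | 1.5% | 80.9% | 81.5% |
| 1.0 | 6% | 81.8% | 84.8% |
| 1.5 | 16% | 83.6% | 90.3% |

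Putting the 20/19 factor into the split of the total SD changes the last two rows only slightly (82.0% v 85.0%, and 84.0% v 90.8%).

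**Step 5: break-even.** Dropping from 19 to 18 df raises the critical value by a factor of 1.0038. The interval widths are equal when d/s = √((1.0038² − 1) × 4 × 19/20) ≈ 0.17, which is about 0.25 points at s = 1.5. Below that, adjustment gains nothing.

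**Step 6: the other reading of 1.5.** If 1.5 were the SD within each sex, pooled against adjusted power would be 80.0% v 80.5% at d = 0.5 and 77.6% v about 80.5% at d = 1.0. Section 4.9.2 does not describe the figure that way.

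**Step 7: the Wilcoxon option.** The planned signed-rank test also pools the sexes. The obvious replacement, a signed-rank test stratified by sex, does worse in simulation: 76.6% v 78.8% for the planned Wilcoxon at d = 0, and 72.1% v 79.5% at d = 1.0.

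**The case against.** A paired t-test on 20 within-subject differences is standard and valid, every subject is their own control, and nothing in the documents suggests that the device works differently in men and women. A three-point gain in power needs a gap of 1.0, as large as the whole target effect. All of this stands, and it is why the point is minor.

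Four stronger readings are tempting, and the documents do not support them.

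- *Any sex difference costs power.* It does not. Up to about 0.25 points nothing is gained by adjusting, and at 0.5 points the gain is about 0.6 power points. A difference in pain level alone cancels in the pairing.
- *The 80% in section 4.9.2 is overstated.* As written, 1.5 is the SD of all paired differences and can already contain a sex gap. The planned t-test then exceeds 80% in every row of the table.
- *The 5% error rate is wrong.* With an overall mean of zero and a gap of 1.0, the pooled t-test rejects 3.8% of the time. That requires the device to help one sex by 0.5 points and worsen pain in the other by the same amount. If it does nothing in either sex, the gap is zero and the t-test has its nominal 5%. The error is never inflated.
- *The within-sex needle assignment shows that all three tests should be stratified.* That assignment concerns IM only and serves its own stated purpose of balance. For fingerstick and SC the argument rests on the 10/10 quota alone. The quota is also not useless as things stand, since it gives men and women equal weight in the mean.

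**Conclusion.** This is a cheap improvement, not an error. The planned t-test is unbiased, does not inflate type I error and reaches its stated power. If the device effect differs materially between men and women, its standard error is too wide, by about 6% at a gap of 1.0 point and 16% at 1.5, and roughly 3 to 7 power points are forgone. If the gap is small, the gain is negligible or nil. The sizes rest on normal differences, a total SD of 1.5, a completed 10/10 split and an assumed gap.

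**What to change.** In section 4.9.1, for each site:

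- Regress the paired difference on sex coded −1/2 and +1/2, and test the intercept as the device effect. With 10 and 10 the intercept equals the plain mean difference, so the estimand is unchanged. Residual df are 18 for fingerstick and SC.
- For IM, also include needle gauge coded −1/2 and +1/2, since it is assigned within sex. This leaves 17 df.
- Report the men-minus-women contrast with a 95% CI, labelled exploratory. With 10 per sex it will be imprecise.
- Judge normality on the model residuals. If it fails, keep the same estimate and use a bootstrap interval resampled within sex. Name the studentised form: a simple percentile interval is short with 10 per stratum, by about √(9/10) × 1.96/2.10 = 0.89 of the t-based width. Do not substitute a sex-stratified signed-rank test, which loses power.

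This changes SAP wording only; sex is already recorded and the gauge assignments must be documented. It needs no extra subjects or procedures. If the effects do not differ, the cost is one degree of freedom (two for IM). By the noncentral t of step 1, power goes from 80.7% to 80.5% on 18 df and 80.2% on 17 df, still above the stated 80%.
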